4. CHANGES IN THE PLANNED ANALYSIS OF THE STUDY

Changes added to the TSAP since the protocol are:

- Addition of Screened Set to the Patients sets analysed (see [Section 6.3](#))
- Missing data rules for National Institutes of Health stroke scale (NIHSS), baseline creatinine clearance, modified Rankin Scale, and disabling stroke were added (see [Section 6.6](#))

Additional changes added to the TSAP as a result of Amendment 1 are:

- Important protocol violation (IPV) clarified, separating atrial fibrillation > 6 minutes and cardiac monitoring < 20 hours into distinct IPVs (A1.1, A1.2) (see [Table 6.2: 1](#))
- ECG analyses were modified based on changes to data collection (see [Section 7.8.4](#))

Additional changes added to the TSAP as a result of Amendment 2 are:

Additional changes added to the TSAP as a result of local Japanese Amendment are:

- Clarification that in Japan, the criteria for major bleed includes transfusion of 4.5 units or more of blood (text added to [Section 5.4](#) that includes those details, but does not change original protocol definition of major bleeds)

5. ENDPOINTS

5.1 PRIMARY ENDPOINT

The primary endpoint, as defined in the CTP, Section 5.1, is time to first recurrent stroke (ischemic, hemorrhagic and unspecified).

5.2 SECONDARY ENDPOINTS

5.2.1 Key secondary endpoints

The key secondary efficacy endpoints are (both time to event endpoints):

- Ischemic stroke
- Composite endpoint of non-fatal stroke, non-fatal MI and cardiovascular death

5.2.2 (Other) Secondary endpoints

Other Secondary efficacy endpoints (all time to event endpoints):

- Disabling stroke (modified Rankin Scale ≥ 4 , as determined 3 months after recurrent stroke)
- All-cause death

5.4 OTHER VARIABLES

Safety endpoints will be used as defined in the CTP, Section 5.2.1.

Major bleeds will be defined according to the ISTH definition of a major bleed, as follows (R05-0344).

- Symptomatic bleeding in a critical area or organ, such as intracranial, intraspinal, intraocular, retroperitoneal, intra-articular or pericardial, or intramuscular with compartment syndrome,

and/or

- Bleeding associated with a reduction in hemoglobin of at least 2g/dL (1.24mmol/L), or leading to transfusion of two or more units of blood or packed cells (equivalent to 4.5 or more units in Japan) (Bleeding should be overt and the hemoglobin drop should be considered to be due to and temporally related to the bleeding event)

and/or

- Fatal bleed

6. GENERAL ANALYSIS DEFINITIONS

6.1 TREATMENTS

Treatment periods are the on-treatment period, defined to start on the first day of treatment and end on the last day of study medication intake plus 6 days or date of death, if earlier, and the post-treatment period, defined to start 7 days after last intake of randomized study drug and end on the date of trial completion, or death, whichever comes first. If no data indicating that the patient is alive are recorded after the last day of study medication intake plus 6 days, then there is no post-treatment period. The screening period is defined as the date of informed consent until the day before first intake of study medication.

Patients will be analyzed in the treatment group as randomized regardless of treatment misallocations. Randomized treatment groups are dabigatran etexilate (merged group of both 110 mg and 150 mg) and acetylsalicylic acid (ASA).

Additional treatment comparisons using baseline assigned dose (DE 110, DE 150, ASA) will be analyzed for primary and secondary efficacy endpoints (and components) plus

Safety endpoints will also be compared by baseline assigned dose (DE 110, DE 150, ASA). These analyses will be descriptive and will include the main safety endpoint major bleeding, as well as life-threatening, fatal, any bleed, intracranial hemorrhage,

Descriptive statistics will be used for these analyses because these dose groups are not randomized.

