4. TREATMENTS

4.1 TREATMENTS TO BE ADMINISTERED

4.1.1 Identity of BI investigational product and comparator product(s)

The investigational product DE, the comparator ASA and respective matching placebos will be supplied by Boehringer Ingelheim Pharma GmbH & Co. KG, Germany. The composition of these drugs capsules are as follows:

Table 4.1.1: 1 Dabigatran etexilate (Investigational drug)

Substance:	Dabigatran etexilate
Brand name:	Pradaxa®
Pharmaceutical formulation:	Capsule
Source:	Boehringer Ingelheim Pharma GmbH & Co. KG, Germany
Unit strength:	110 mg, 150 mg
Total Daily dose:	220 mg or 300 mg
Route of administration:	per os (oral) (p.o.)
Posology:	1 capsule, b.i.d. (Section 4.1.4)

The main excipients of the dabigatran capsule include tartaric acid, acacia, hypromellose, dimeticone, talc, and hydroxylpropyl cellulose, HPMC (hydroxylpropylmethylcellulose) capsule shell consisting of titanium dioxide (E171) FD&C Yellow 6/Sunset Yellow (E110), FD&C Blue 2 /Indigo Carmine (E132) hypromellose, carrageenan and potassium chloride.

Table 4.1.1: 2 Placebo matching dabigatran

Substance:	placebo matching dabigatran 150 mg placebo matching dabigatran 110 mg
Brand name:	not applicable
Pharmaceutical formulation:	Capsule
Source:	Boehringer Ingelheim Pharma GmbH & Co. KG, Germany
Unit strength:	0 mg
Total Daily dose:	not applicable
Route of administration:	p.o.
Posology:	1 capsule, b.i.d. (Section 4.1.4)

Table 4.1.1: 3 Acetylsalicylic acid

Substance:	Acetylsalicylic acid (immediate-release tablet)
Brand name:	Acetylsalicylsäure (ASS) 100mg HEXAL
Pharmaceutical formulation:	Tablet
Source:	Hexal AG, Germany
Unit strength:	100 mg
Total Daily dose:	100 mg
Route of administration:	p.o.
Posology:	1 tablet, once daily (q.d)

Table 4.1.1: 4 Placebo matching ASA

Substance:	placebo matching ASA (ASA-placebo)
Brand name:	not applicable
Pharmaceutical formulation:	Tablet
Source:	Boehringer Ingelheim Pharma GmbH & Co. KG, Germany
Unit strength:	0 mg
Total Daily dose:	not applicable
Route of administration:	p.o.
Posology:	1 tablet, once daily (q.d)

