4.1.3 Selection of doses in the trial

The doses of DE selected for this trial are the same as those used in RE-LY, the Phase III trial for SPAF. In RE-LY, a dose of DE 110 mg b.i.d. was shown to be comparable to warfarin (INR level 2.0–3.0) for preventing strokes and SE, and superior when considering major bleeding risk with a relative risk reduction of 20% ([U09-3249-02](#)). Moreover, there was an approximately 60% reduction in intracranial hemorrhage with both dosages of DE.

The overarching goal related to this exposure level is to achieve superiority in efficacy over ASA with no clinically meaningful excess in bleeding with DE. To achieve this, the dosing instructions applied in this trial are intended to provide homogeneous exposure distribution among patients included into this trial. This means that patients at higher risk of bleeding (i.e. patients aged 75 years or older, or with moderate renal impairment) will receive the lower dose of 110 mg b.i.d. and will achieve an exposure comparable to those patients without these risk factors.

The average exposure across all patients (dabigatran trough levels) will range between the trough levels achieved with 110 mg b.i.d. (median of 66 ng/ml) in the RE-LY trial and the level obtained with 150 mg b.i.d. in RE-LY (median of 93 ng/ml): By utilizing the PK experience from RE-LY ([U09-3249-02](#)) and by considering patients characteristics such as age and renal function from a secondary stroke population included in the PROFESS study ([U08-3667-01](#)), PK modeling has shown that the dosing algorithm in this study will result in a median of plasma trough levels of approximately 77 ng/mL. This exposure is expected to provide superior efficacy over the antiplatelet agent ASA with a comparable low rate of intracranial hemorrhage and the overall ability to deliver an optimal balance of efficacy and safety across the population in the trial.

To obtain the targeted exposure, dabigatran dosing will be adjusted for age and renal function, as follows: Patients will be assigned to DE dose of 150 mg b.i.d., unless they are 75 years or older, or have a CrCl of ≥ 30 to < 50 ml/min, in which case they will receive DE 110 mg b.i.d.

Patients assigned to DE, who initially qualify to receive 150 mg b.i.d., will be down-titrated to 110 mg b.i.d. if their CrCl deteriorates to ≥ 30 - < 50 mL/min, if they experience a GI bleed, or the patient becomes 75 years old during the course of the trial. The patient will be

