asked to return their 150 mg medication and receive 110 mg at an unscheduled visit as soon as possible if their titration is due to drop in CrCl or GI bleed. Patients who turn 75 years old during the trial will receive the 110 mg dose at their next scheduled visit. Patients will only have the option to change the dose once, i.e. there will be no up-titration from 110 to 150 mg b.i.d. if renal function recovers.

Using the characteristics of higher risk populations, modeling shows comparable exposure (median trough concentration of 89 ng/ml) in patients receiving DE 110 mg b.i.d. compared to patients without these risk factors receiving DE 150 mg b.i.d. (median trough concentration of 74 ng/ml) in this trial. Therefore it is concluded that dose adjustment to DE 110 mg b.i.d. may optimize the risk-benefit profile in patients at higher risk of bleeding.

The 100 mg dose of ASA was selected based upon recommendations in current guidelines and because this dosage is widely available and acceptable to most clinicians around the world. Patients assigned to ASA will not change their ASA dose during the course of the trial.

Because assignment of ASA vs. DE is blinded, all patients will have their DE down-titrated via IRT under the age, GI bleed or renal function conditions mentioned above. It will be unknown if the DE kits are active or placebo.

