4.1.4 Drug assignment and administration of doses for each patient

Drug is dispensed by the Investigator, study coordinator, or pharmacist, depending on the study organization. IRT will be used to assign an appropriate active study drug and placebo to the patient. The site staff will be prompted to notify the IRT of all relevant information to identify patient as well as assign appropriate DE dose according to the algorithm (i.e. according to age, renal function and GI bleed that occurs during the course of the trial).

Study drug is dispensed every three months over the first year and every 6 months thereafter at regularly scheduled study visits (except the EOT and Final Visit). Study drug kits will contain enough supply to last until the next visit plus some overage.

Patients randomized to active treatment with DE will also receive an ASA placebo kit. Patients randomized to active treatment with ASA will also receive a DE placebo kit.

Patients will be instructed on the importance of taking both the active and placebo treatment because they will not know which one is active versus placebo.

Adjustments of DE dose can occur once per patient and will be managed within the IRT system.

Dabigatran etexilate capsules should be taken in the morning and in the evening, at the same time every day. The interval between doses should be as close to 12 hours as possible. If a dose of DE is not taken at the scheduled time, the dose should be taken as soon as possible on the same day; the missed dose should be skipped, if it cannot be taken at least 6 hours before the next scheduled dose. The next dose of DE should not be doubled to make up for a missed dose. If a dose of ASA or matching placebo is not taken at the scheduled time, the dose

should be taken as soon as possible on the same day; the missed dose should be skipped if it cannot be taken at the same day. For visits with pharmacokinetic trough sampling (Visit 1, Visit 3 and Visit 6 as outlined in the [Flow Chart](#)) patients should take that morning dose of trial medication at the study site (after the blood sample has been taken) to ensure the pharmacokinetic sample is taken at trough, 10:00-16:00 hours after the last drug intake and prior to the next drug intake.

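### SAP 6.1 sets each dabigatran dose beside one undivided ASA group, although ASA split by baseline placebo strength would give a randomised comparator

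*SAP*

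**What the plan says.** SAP 6.1 defines the randomised groups as dabigatran (both doses merged) and ASA. It then adds by-dose displays: "Additional treatment comparisons using baseline assigned dose (DE 110, DE 150, ASA) will be analyzed for primary and secondary efficacy endpoints". For bleeding it says "Safety endpoints will also be compared by baseline assigned dose (DE 110, DE 150, ASA"), naming major, life-threatening, fatal and any bleeding and intracranial haemorrhage. It gives the status of these displays: "Descriptive statistics will be used for these analyses because these dose groups are not randomized". No model is named for them. The covariates of the SAP 7.4 Cox model (age cut at 75, CrCl cut at 50, prior stroke or TIA) are not mentioned in 6.1.

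Protocol 4.1.3 fixes the dose: "Patients will be assigned to DE dose of 150 mg b.i.d., unless they are 75 years or older" or have a CrCl of 30 to below 50 mL/min. It also states that "patients at higher risk of bleeding (i.e. patients aged 75 years or older, or with moderate renal impairment) will receive the lower dose".

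The ASA arm carries the same information. Protocol 4.1.1 lists "placebo matching dabigatran 150 mg placebo matching dabigatran 110 mg", and Protocol 4.1.4 says "Patients randomized to active treatment with ASA will also receive a DE placebo kit". Protocol 5.2.3 makes the Visit 1 CrCl determine the strength of dabigatran or of its placebo. For later changes, Protocol 4.1.3 says that "all patients will have their DE down-titrated via IRT under the age, GI bleed or renal function conditions mentioned above".

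**The concern.** The natural reading of the three-group list, though no sentence says so outright, is that each dose is set beside all ASA patients. That mixes dose with age and renal risk. If the patients eligible for 110 mg have the higher underlying risk, the same treatment effect at both doses will look weaker at DE 110 and stronger at DE 150, in plain event rates as well as in unadjusted hazard ratios. The protocol supports a higher risk for bleeding. For stroke, the size and direction of the difference are assumptions.

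These are the displays in which a reader will look for evidence on dosing by age and renal function, which is part of the trial objective. A false dose pattern in efficacy or bleeding could be taken for a real one. A better comparator is already in the data and the visible plan does not use it.

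**Working it through.** **The plan's own figure.** With 353 events, HR 0.70, 1:1 allocation and two-sided 0.05, power is Φ(√353/2 × |ln 0.70| − 1.96) = 0.918, against about 92% in Protocol 7.6. The event count and effect size are therefore used as given.

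**Is a randomised comparator available?** Age and CrCl are known at Visit 1 and randomisation is at Visit 2 (Protocol 6.2.2). The interactive response system applies the dose rule blind to arm. Baseline strength is therefore a pre-randomisation characteristic of every patient, and DE versus ASA within a strength is a randomised subgroup comparison. This holds for baseline strength only. Later down-titration is post-randomisation.

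**Inputs**
- ASA stroke rate: about 4.1% per year (Protocol 7.6).
- Assumed true HR: 0.70 at both doses for stroke (the design value) and, for illustration, 1.5 at both doses for bleeding.
- Assumed share on the 110 mg strength, p = 0.20. It comes from the modelled median troughs in Protocol 4.1.3, (77 − 74)/(89 − 74) = 0.20. Medians do not mix exactly linearly, so 0.15 and 0.30 are also shown.
- Assumed risk ratio r of 110-eligible to 150-eligible patients. The documents do not give it; the range used is 0.8 to 1.5.

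**Rates per 100 patient-years.** Let m = (1 − p) + p·r. ASA with 150 mg placebo has rate 4.1/m, ASA with 110 mg placebo 4.1·r/m, and DE 0.70 times each.

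| r | m | Three-group display: DE 110 / ASA / DE 150 | Matched 110: DE vs ASA | Matched 150: DE vs ASA |
|---|---|---|---|---|
| 1.25 | 1.05 | 3.4 / 4.1 / 2.7 | 3.4 vs 4.9 | 2.7 vs 3.9 |
| 1.5 | 1.10 | 3.9 / 4.1 / 2.6 | 3.9 vs 5.6 | 2.6 vs 3.7 |

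**Hazard ratios against all ASA.** Unadjusted, DE 110 shows HR·r/m and DE 150 shows HR/m. The adjusted column is a large-sample Poisson fit on expected counts with terms for DE 110, DE 150, age ≥75 and CrCl <50. It assumes 17% aged ≥75, with CrCl <50 in 30% of those and 4% of the others (share 0.17 + 0.83 × 0.04 = 20.3%), and risk r if either condition applies. Prior stroke or TIA is left out.

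| True HR | r | Unadjusted DE 110 / DE 150 | Adjusted DE 110 / DE 150 | Matched strength |
|---|---|---|---|---|
| 0.70 | 0.8 | 0.58 / 0.73 | 0.68 / 0.70 | 0.70 / 0.70 |
| 0.70 | 1.0 | 0.70 / 0.70 | 0.70 / 0.70 | 0.70 / 0.70 |
| 0.70 | 1.25 | 0.83 / 0.67 | 0.72 / 0.69 | 0.70 / 0.70 |
| 0.70 | 1.5 | 0.95 / 0.64 | 0.74 / 0.69 | 0.70 / 0.70 |
| 1.5 | 1.25 | 1.79 / 1.43 | 1.56 / 1.48 | 1.50 / 1.50 |
| 1.5 | 1.5 | 2.05 / 1.36 | 1.61 / 1.46 | 1.50 / 1.50 |

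At r = 1.5 and true HR 0.70, a 15% share gives 0.98 / 0.65 unadjusted and a 30% share 0.91 / 0.61. If the age and CrCl effects multiply, the adjusted model returns 0.70 / 0.70 exactly.

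**Precision at p = 0.20, r = 1.5, HR 0.70.** ASA events are 353/1.7 = 207.6 and DE events 145.4. The 110 stratum holds 0.20 × 1.5/1.1 = 27.3% of each: 39.6 DE and 56.6 ASA.
- Matched 110: SE = √(1/39.6 + 1/56.6) = 0.207; 95% CI about 0.47 to 1.05.
- DE 110 against all ASA, unadjusted: SE = √(1/39.6 + 1/207.6) = 0.173.
- DE 110 against all ASA, adjusted for age and CrCl: SE = 0.202 from the Poisson fit.
- Matched 150: 105.7 and 151.0 events; SE = √(1/105.7 + 1/151.0) = 0.127; 95% CI about 0.55 to 0.90.

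**The case against.** The strongest reply is that the SAP already discloses the problem: the displays are descriptive, called non-randomised, and outside the test hierarchy. Moreover, every time-to-event model visible in the SAP (7.4, 7.5 and 7.8) carries the age and CrCl covariates. If by-dose hazard ratios come from that model, the shift for DE 110 at r = 1.5 is ln(0.737/0.70) = 0.05, about a quarter of its standard error of 0.202. This stands as far as it goes. But 6.1 does not invoke the model, plain event rates are not adjusted by it, and the label does not change what the rates show.

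Parts of SAP 6.1 and some contents entries are blacked out, so age or renal subgroup analyses may exist there. That cannot be checked.

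The inputs p and r are assumed, and at r = 1 there is no bias. That is why ranges are shown.

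Three limits on the remedy also stand:
- The main bleeding analysis uses the treated set on treatment, so the full protection of randomisation applies only to the randomised-set analyses.
- No stratification by strength is described, so chance imbalance within a strength is possible.
- Patients may be randomised on local laboratory results while analyses use central Visit 1 values, and SAP 6.6 allows an on-treatment CrCl when baseline is missing. The CrCl covariate can therefore disagree with the strength dispensed. This complicates the model slightly and is also a reason to group by assigned strength.

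**Conclusion.** The concern holds. In the visible text, the by-dose displays use one undivided ASA group with no stated adjustment, and dose is determined by age and renal function. On the assumptions above (20% share, r = 1.25 to 1.5, equal effect at both doses), a true HR of 0.70 would appear unadjusted as 0.83 to 0.95 for DE 110 and 0.67 to 0.64 for DE 150. With the SAP 7.4 covariates most of this goes, leaving 0.72 to 0.74 and 0.69. Matching on baseline placebo strength removes it in every case examined. The consequence is limited to supplementary efficacy and bleeding displays; the primary test, the hierarchy and alpha are untouched. It should be changed because the remedy is cheap and the data are already collected.

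**What to change.** In SAP 6.1, define the ASA comparator by the matching-placebo strength assigned at baseline by the interactive response system. Present, descriptively, DE 110 versus ASA with 110 mg placebo and DE 150 versus ASA with 150 mg placebo, with event rates, hazard ratio and 95% CI from the SAP 7.4 Cox model, for the efficacy and bleeding endpoints already listed. State that grouping is by baseline strength, not by strength after down-titration. Note that under the dosing rule age and CrCl category do not vary within the 150 mg strength, so there the model reduces to treatment and prior stroke or TIA, apart from patients whose analysed CrCl differs from the value used for dosing. If the display against all ASA is kept, use the age- and CrCl-adjusted model and label it as not a randomised comparison. DE 110 versus DE 150 stays non-randomised either way.

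The cost is a few lines of SAP text and one grouping variable. The comparator in the 110 mg stratum is smaller, but the loss of precision is material only against the unadjusted display (SE 0.207 versus 0.173). Against the adjusted model it is 0.207 versus 0.202.

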6.2 IMPORTANT PROTOCOL VIOLATIONS

Table 6.2: 1 contains important protocol violations that will be listed in the clinical trial report.

Table 6.2: 1 Important protocol violations

Category/ Code	Description	Example/Comment	Excluded from
A	Entrance criteria not met		
A1.1	Atrial fibrillation duration > 6 minutes	AFib duration > 6 minutes	None
A1.2	Cardiac monitoring < 20 hours	Cardiac monitoring < 20 hours	None
A2.1	Conditions not consistent with diagnosis of ESUS	Inclusion criteria 2A, 3 (IN2A, IN3), Exclusion criterion 1,2,4,5,21 (EX1, EX2, EX4, EX5, EX21), and IN2 (programmed for patients without ESUS)	None
A2.2	Any indication that requires treatment with anticoagulant	EX3	None
A2.3	Primary intracerebral hemorrhage on qualifying neuroimaging	EX6	None
A2.4	Conditions associated with risk of bleeding	EX7, EX7A	None
A2.5	History of symptomatic intracranial hemorrhage	EX8, EX8A	None
A2.6	Renal impairment; CrCL<30mL/min	EX9	None
A2.7	History of hypersensitivity to dabigatran or ASA	EX10	None
A2.8	Participation in another trial with investigational drug or device within past 14 days	EX16, EX16A	None
A2.9	Conditions that would not allow safe trial participation	EX18, EX18A	None
A2.10	Active liver disease	EX19	None
A2.11	Severe glucose-6-phosphate dehydrogenase deficiency	EX20	None
A2.12	Previous participation (receipt of randomized treatment) in this trial	Manual PV	None
B	Informed consent		
B1	Informed consent not available/not done	Informed consent date missing	All
B2	Informed consent too late	Informed consent date was after Visit 1 date	None

Table 6.2: 1 (continued) Important protocol violations

Category/ Code	Description	Example/Comment	Excluded from
C	Trial medication and randomization		
C1	Incorrect trial medication taken	Medication kit assigned not matching treatment patient was randomized to (cross-treatment) and/or not matching IVRS assignment	None
C2	Randomization not followed	Date of first trial medication before date of randomization	None
C3.1	Treatment not interrupted when required	Study drug not interrupted when AF diagnosed or CrCL < 30 mL/min	None
C3.2	Non-compliance	Cumulative compliance <80% or >120% (see Section 7.3)	None
C4	Medication code broken inappropriately	Manual PV	None
C5	Incorrect dose adjustment (on wrong medication > 50% of the time)	Patient on incorrect dose according to age, renal criteria, in-trial GI bleed	None
D	Concomitant medication		
D2	Prohibited medication use	See CTP Section 4.2.2.1	None

6.3 PATIENT SETS ANALYSED

- Screened set (SCR):
This patient set includes all patients who signed informed consent and completed at least some screening procedures.
- Randomized set (RS)
This patient set includes all randomized patients, whether treated or not.
- Treated set (TS):
This patient set includes all patients who were documented to have taken at least one dose of investigational treatment. The start date of the observation period for this analysis set is the date of first intake of trial medication.

The final decision as to whether a patient is included in or excluded from each analysis set will be taken before database lock in a blinded manner and will be documented in the minutes of the Blinded Report Planning Meeting (BRPM) or Database Lock Meeting.

Analyses will be performed as outlined in [Table 6.3: 1](#).

Table 6.3: 1 Patient sets analysed

Class of endpoint	Patient set		
	Screened set	Randomized set	Treated set
Primary endpoints		X	S ¹
Secondary endpoints		X	
Safety endpoints		S ¹	X
Patient disposition	X		

¹ S=Sensitivity analyses (see [Section 7.4](#) and [7.8](#))

Two analysis periods are defined:

- Full follow-up: from date of randomization until the date of last contact (see [Section 6.8](#)), including all observed time on and off trial medication
- On-treatment: from the date of first treatment intake until the date of discontinuation of trial medication + 6 days (or death, if death occurs earlier)

